6.8.3 Intraocular Pressure (IOP)

The IOP must be measured only after the biomicroscopic exam is completed and must be measured prior to pupil dilation. IOP will be taken by qualified study site personnel with the subject seated. Every effort should be made to ensure that the same study site personnel uses the same device for IOP measurement for a given subject. A Goldmann applanation tonometer affixed to a slit-lamp is the preferred device for IOP measurement.

Clinical Study Protocol: AR-15512-CS201, Amendment 4

6.9 Adverse Events Assessments

6.9.1 Performing Adverse Event (AE) Assessments

Qualified study staff responsible for assessing AEs will be listed on the Site Authorization and Delegation Log. This includes assessment of AE severity and relationship to treatment. AE information may be volunteered by the subject or solicited by study personnel through non-leading questions.

All AEs occurring during the study, regardless of the assumption of causal relationship, must be documented on the respective CRF. AEs should be documented from the time the subject provides informed consent and throughout the study. If a serious or non-serious AE/adverse reaction is unresolved at the time of the exit date, efforts will be made to follow up until the AE/adverse reaction is resolved or stabilized, the subject is lost to follow-up, or there is other resolution to the event.

Documentation of AEs/adverse reactions will include start date and stop date, severity, relationship, action(s) taken, seriousness, and outcome.

6.9.2 Adverse Event Definitions

The following definitions of terms apply to this section:

- Adverse event (AE): any untoward medical occurrence associated with the administration of the drug in humans, whether or not considered drug related.
- Suspected adverse reaction (SAR): any AE for which there is a reasonable possibility that the administration of the drug caused the AE. For the purposes of Investigational New Drug (IND) safety reporting, "reasonable possibility" means there is evidence to suggest a causal relationship between the administration of the drug and the AE. SAR implies a lesser degree of certainty about causality than adverse reaction, which means any AE caused by the administration of a drug.
- Life-threatening AE or life-threatening SAR: an AE or SAR is considered "life-threatening" if, in the view of either the Investigator or Sponsor, its occurrence places the subject or subject at immediate risk of death. It does not include an AE or SAR that, had it occurred in a more severe form, might have caused death.
- Serious adverse event (SAE) or serious suspected adverse reaction (SSAR): an AE or SAR is considered "serious" if, in the view of either the Investigator or Sponsor, it results in any of the following outcomes: Death, a life-threatening or sight-threatening AE, in subject hospitalization or prolongation of existing hospitalization, a persistent or significant incapacity or substantial disruption of the ability to conduct normal life functions, or a congenital anomaly/birth defect. Important medical events that may not result in death, be life-threatening, or require hospitalization may be considered serious when, based upon appropriate medical judgment, they may

jeopardize the subject and may require medical or surgical intervention to prevent one of the outcomes listed in this definition. Examples of such medical events include allergic bronchospasm requiring intensive treatment in an emergency room or at home, blood dyscrasias, or convulsions that do not result in subject hospitalization, or the development of drug dependency or drug abuse.

• Unexpected AE or unexpected SAR: an AE or SAR is considered "unexpected" if it is not listed in the Investigator's Brochure or is not listed at the specificity or severity that has been observed; or, if an Investigator's Brochure is not required or available, is not consistent with the risk information described in the general investigational plan or elsewhere in the current application, as amended. For example, under this definition, hepatic necrosis would be unexpected (by virtue of greater severity) if the Investigator's Brochure referred only to elevated hepatic enzymes or hepatitis. Similarly, cerebral thromboembolism and cerebral vasculitis would be unexpected (by virtue of greater specificity) if the Investigator's Brochure listed only cerebral vascular accidents. "Unexpected," as used in this definition, also refers to AEs or SARs that are mentioned in the Investigator's Brochure as occurring with a class of drugs or as anticipated from the pharmacological properties of the drug but are not specifically mentioned as occurring with the particular drug under investigation.

Note: Any medical condition present prior to informed consent and prior to administration of the study medication which remains unchanged or improved should not be recorded as an AE at subsequent visits.

Note: If an event occurs after informed consent but prior to subject enrollment and the commencement of study medication, it should be recorded as an AE. Any change in the health status after commencement of study medication should be recorded as treatment emergent AEs.

6.9.3 Timing for Reporting Adverse Events

The AEs occurring during the study must be documented, regardless of the assumption of a causal relationship. AEs should be documented from the time the subject provides informed consent until subject participation in the study has been completed. If a serious or non-serious AE/adverse reaction is unresolved at the time of exit, efforts will be made to follow up until the AE/adverse reaction is resolved or stabilized, the subject is lost to follow-up, or there is other resolution to the event. These follow-up visits will be documented.

When recording an AE, the following information should be provided on the study AE CRF:

- 1. Action Taken with Study Drug:
 - None
 - IP Discontinued
 - IP Interrupted
- 2. AE Outcome:
 - Fatal

- Not Recovered/Not Resolved
- Recovered/Resolved
- Recovered/Resolved with sequelae
- Recovering/Resolving
- Unknown/Lost to follow-up

6.9.4 Severity

Severity of an AE is defined as a qualitative assessment of the level of discomfort or the degree of intensity of an AE as determined by the Investigator or reported to them by the subject. The assessment of severity is made irrespective of study medication relationship or seriousness of the event and should be evaluated according to the following scale:

- 1 = Mild: present and noticeable, but not distressing, and no disruption of normal daily activities
- 2 = Moderate: bothersome, discomfort sufficient to possibly reduce or affect normal daily activity
- 3 = Severe: incapacitating, with inability to work or perform normal daily activity

A change in increased severity for a reported AE will require a stop date for the previous severity and a new start and stop date for the new severity. For example, a change in severity may go from mild to moderate, or from moderate to severe. In either case, the start and stop dates should be recorded.

Note: A severe AE is not the same as a serious AE. Seriousness of an AE (NOT severity) serves as a guide for defining regulatory reporting obligations (See Section 6.9.7 for further information on SAEs, SSARs, and SUSARs).

6.9.5 Relationship

A relationship between the AE and the study medication or study procedure will be determined by the Investigator, as applicable for each AE using these explanations:

- Not Related: The event is clearly related to other factors such as subject's clinical condition, therapeutic interventions, concomitant disease, or therapy administered to the subject and does not follow a known response pattern to the product or procedure.
- Unlikely Related: The event is most probably caused by other etiologies such as subject's underlying condition, therapeutic intervention, or concomitant therapy; or the delay between administration and the onset of the AE is incompatible with a causal relationship. Therefore, there is not a reasonable possibility that the AE was caused by the product or procedure.

- Possibly Related: The event follows a reasonable, temporal sequence from the time of study medication administration or study procedure and/or follows a known response pattern to the product or procedure but could have been produced by other factors such as the subject's clinical state, therapeutic interventions, or concomitant therapy administered to the subject.
- Related: The event follows a reasonable, temporal sequence from the time of study medication administration or study procedure and/or follows a known response pattern to the product or procedure and cannot be reasonably explained by other factors such as subject's clinical state, therapeutic interventions or concomitant therapy administered to the subject, and either occurs immediately following study medication administration or procedure, or improves on stopping the study medication, or reappears on repeat exposure, or there is a positive reaction at the application site.

6.9.6 Expectedness

AEs or SARs are considered "unexpected" if they **are not** listed in the Investigator's Brochure for AR-15512 or **are not** listed at the specificity or severity that has been observed. "Unexpected," as used in this definition, also refers to AEs or SARs that **are** mentioned in the Investigator's Brochure as occurring with this class of drugs or as anticipated from the pharmacological properties of AR-15512 and **are not** specifically mentioned as occurring with the IP. The AEs and adverse reactions that are both unexpected and serious should be reported in an expedited fashion to the Sponsor and / or contract research organization (CRO).

6.9.7 Serious Adverse Events (SAEs), Serious Suspected Adverse Reactions (SSARs) or Suspected Unexpected Serious Adverse Reactions (SUSARs)

6.9.7.1 Reporting SAEs or SSARs

An Investigator must immediately (i.e., within 24 hours) report any SAE or SSAR (see Section 6.9.2 for definitions) to the Sponsor or its CRO representative, whether or not considered drug-related, including those listed in the protocol or Investigator's Brochure. The Investigator must use the SAE report form and include an assessment of whether there is a reasonable possibility that the drug caused the event. The Investigator must report any SAE or SSAR that occurs or is observed during the study. In case of incomplete information, the Investigator must provide follow-up information as soon as possible, again using the SAE report form.

SAEs and SSARs must be reported to the IRB according to the IRB requirements.

6.9.7.2 Reporting Serious Unexpected Suspected Adverse Reactions (SUSARs)

The Investigator must immediately (i.e., within 24 hours) report SUSARs that occur or are observed during the study or at the subject's last study visit. In the event of SUSAR, the site must notify the Medical Monitor for the study using the SAE report form within 24 hours of

notification, observation, or occurrence of the SUSAR, whether or not complete information is available. In the case of incomplete information, the Investigator must provide follow-up information as soon as possible using the SAE report form.

Reports will be evaluated by the Medical Monitor. The FDA, IRB and Investigators at each of the study sites will be informed as required.

6.9.8 Pregnancy Reporting

Pregnancies occurring in subjects enrolled in the study or in their partners must be reported and followed to outcome. While pregnancy itself is not considered to be an AE or SAE, pregnancy reports are tracked by the Sponsor or its CRO representative. Premature terminations including miscarriage, spontaneous abortion, or elective termination of a pregnancy for medical reasons will be reported as an SAE. Other pregnancy complications should be reported as SAEs, if they meet serious criteria. Should the pregnancy result in a congenital anomaly or birth defect, a separate SAE report must be submitted. Furthermore, all neonatal deaths that occur within 30 days of the birth should be reported as SAEs, without regard to causality.

The Investigator must complete the pregnancy report form and fax or email the form to the Sponsor or its CRO representative within 1 business day of knowledge of the pregnancy. Following delivery or termination of pregnancy, the pregnancy report form is to be completed and submitted by fax or email to the Sponsor or its CRO representative.

Pregnancies occurring from the time of consent through the subject's last study visit are to be reported.

6.9.9 Reporting Serious Adverse Events, Serious Suspected Adverse Reactions (SSARs) or Suspected Unexpected Serious Adverse Reactions (SUSARs)

The Investigator must report an SAE, SSAR, or SUSAR occurring at his/her site to the Sponsor or its CRO representative regardless of causality.

6.10 Removal of Subjects from the Study or Investigational Product

6.10.1 Completed Subject

A completed subject is defined as one who completes all planned study treatments and visits.

6.10.2 Non-completing Subject

A non-completing subject is defined as one who exits the study by their own volition or at the discretion of the Investigator, the Medical Monitor, and/or an Aerie Safety Officer/designee. Any subject may decide to voluntarily withdraw from the study at any time without prejudice. If discontinuation of treatment is necessary, the Investigator will make every attempt to complete all subsequent safety assessments listed for the Early Termination Visit.

The subject may also be discontinued from the study for the following reasons:

- AEs (AEs including, in the opinion of the Investigator, clinically relevant laboratory abnormalities, and intercurrent diseases reported by the subject or observed by the Investigator with documentation on the CRF)
- Withdrawal of Consent
- Non-compliance (e.g., non-adherence to scheduled follow-up visits or use of study treatment)
- Lost to Follow-up
- Pregnancy
- Investigator Decision
- Protocol Deviation
- Death
- Other

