- Use of lid heating therapy (i.e., LipiFlow[®], iLUX[®]) or Meibomian gland probing/therapeutic expression within 1 year prior to the Screening visit

Aerie Pharmaceuticals, Inc.

Study Population:

This study is anticipated to enroll approximately 360 subjects with DED so as approximately 324 subjects complete Day 84. The anticipated drop out rate is 10%. To achieve this goal, approximately 1500 subjects may be screened.

Investigational Product, Dose, and Mode of Administration:

BID topical ocular administration of AR-15512 ophthalmic solution 0.0014%, AR-15512 ophthalmic solution 0.003% or AR-15512 vehicle

Duration of Treatment:

Approximately 14 weeks of BID dosing of 1 drop to each of both eyes

Efficacy Assessments:

Primary Assessments:

- Ocular Discomfort Score (ODS) based on Visual Analog Scale (VAS)
- · Anesthetized Schirmer test

Secondary Assessments:

- Ocular Pain Score based on VAS
- SANDE (Symptom Assessment iN Dry Eye) Questionnaire Score
- Eye Dryness Score based on VAS

Safety Assessments:

- Adverse events
- · Hematology, chemistry, and urinalysis
- Best-corrected visual acuity
- Intraocular pressure
- Dilated fundus exam

Statistical Methods:

Sample Size Determination

One hundred and eight (108) ITT population subjects (study eyes) per treatment group yields 90% power to conclude superiority of AR-15512 (0.003% or 0.0014%) over vehicle in the mean change from baseline (CFB) pre-CAE ODS-VAS at Day 28, assuming a true difference (AR-15512 minus vehicle) of -8.5, a common standard deviation of 19.0, and a two-sided alpha = 0.05.

Additionally, 108 ITT population subjects (study eyes) per treatment group yields 90% power to conclude superiority of AR-15512 (0.003% or 0.0014%) over vehicle in the mean CFB in pre-CAE anesthetized Schirmer score at Day 28 assuming a true difference (AR-15512 minus vehicle) of 1.4 mm, a common standard deviation of 3.15 mm, and a two-sided alpha = 0.05.

Accounting for subject discontinuations, approximately 360 total subjects (120 per treatment arm) will be randomized assuming a dropout rate of 10%.

Analyses

AR-15512 Ophthalmic Solution

Clinical Study Protocol: AR-15512-CS201, Amendment 4

Aerie Pharmaceuticals, Inc.

The co-primary efficacy endpoints will be:

- Change from baseline in pre-CAE ODS-VAS at Day 28
- Change from baseline in pre-CAE anesthetized Schirmer score at Day 28

Date of Original Approved Protocol (Rev. 0): 06 August 2020

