7.5 Early Termination Procedures

- Collection of used and unused study treatment
- Concomitant medication review

- AE review
- Pregnancy test (WOCBP only)
- Symptom Questionnaire (VAS) (Ocular Discomfort, Eye Dryness and Ocular Pain)
- SANDE Questionnaire (VAS)
- Ora Calibra Ocular Discomfort Scale (ODS)
- Best-corrected visual acuity
- Slit-lamp biomicroscopy
- Intraocular Pressure
- Dilated Fundus Exam
- Study Exit

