9. PLANNED STATISTICAL METHODS

9.1 Statistical Considerations

9.1.1 General Considerations

Quantitative variables will be summarized using number of subjects (n), mean, median, standard deviation, minimum and maximum. Qualitative variables will be summarized using counts and percentages.

All summaries will be presented by treatment group.

For the purpose of summarization, medical history, concurrent therapies, and AEs will be coded to MedDRA and WHO Drug dictionaries, as appropriate.

Baseline measures are defined as the last non-missing measure prior to the initiation of randomized study treatment. If a measure is taken both pre-CAE® and post-CAE®, baseline will be the time point matched value.

Change from baseline (CFB) will be calculated as visit – baseline; treatment comparisons will be calculated as AR-15512 – vehicle; and pre to post CAE comparisons will be calculated as post-CAE minus pre-CAE.

All primary and secondary analyses will be two-sided at a significance level of 0.05.

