9.3 Determination of Sample Size

One hundred and eight (108) ITT population subjects (study eyes) per treatment group yields 90% power to reject H_{01} in favor of H_{11} and H_{03} in favor of H_{13} and conclude superiority of AR-15512 (0.003% or 0.0014%) over vehicle in the mean CFB pre-CAE ODS VAS at Day 28, assuming a true difference (AR-15512 minus vehicle) of -8.5, a common standard deviation of 19.0, and a two-sided alpha = 0.05.

Additionally, 108 ITT population subjects (study eyes) per treatment group yields 90% power to reject H_{02} in favor of H_{12} and H_{04} in favor of H_{14} and conclude superiority of AR-15512 (0.003% or 0.0014%) over vehicle in the mean CFB in pre-CAE anesthetized Schirmer score at Day 28 assuming a true difference (AR-15512 minus vehicle) of 1.4 mm, a common standard deviation of 3.15 mm, and a two-sided alpha = 0.05.

Accounting for subject discontinuations, approximately 360 total subjects (120 per treatment arm) will be randomized assuming a dropout rate of 10%.

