9.4.1 Intent-to-Treat (ITT) Population

The ITT population includes all randomized subjects. The primary efficacy analysis will be performed on the ITT population. Subjects in the ITT population will be analyzed as randomized.

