8.3.2 Assessment Time Windows

In general, it is intended that all safety and efficacy data (with some exceptions) will be summarized at each scheduled time point collected regardless of assessment time windows. Because subjects may have an early termination visit at any time or may have unscheduled visits, the following conventions will be implemented.

For all by-visit statistical summaries, safety and efficacy data collected at early termination visits will be windowed into a scheduled study visit if the early termination visit falls within a protocol specified visit window. Visit 2 (Day 1) has to be on Day 1. Visit 3 (Day 14) and Visit 4 (Day 28) have a \pm 2-day window. Visit 5 (Day 84) has -5/+2 day window. Unscheduled visits and early termination visits falling out of protocol specified scheduled visit windows will be excluded from summaries.

Version 1.0 Page 28 of 42

[figure not shown]

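### Subjects who stop study drops are not asked for the Day 28 or Day 84 efficacy measurements, and the Early Termination visit omits the anesthetized Schirmer test

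*Protocol*

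**What the plan says.** Protocol 6.10.2 defines the non-completing subject as one who exits the study. Its only instruction on stopping treatment sits inside that definition: "If discontinuation of treatment is necessary, the Investigator will make every attempt to complete all subsequent safety assessments listed for the Early Termination Visit".

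Protocol 6.10.3 adds medical follow-up for subjects who stop because of an adverse event. For those who withdraw consent or are discontinued for non-compliance, it adds a final visit with the ET examinations. Neither sentence mentions Day 28 or Day 84 efficacy assessments.

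Protocol 7.5, "Early Termination Procedures", lists the symptom VAS (which includes ocular discomfort), SANDE and the Ora Calibra ODS, and closes with study exit. The anesthetized Schirmer is not on the list. Its ET cell is also blank in the visit schedules of the protocol (Appendix 4) and the SAP (Appendix 1).

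The primary analysis set is every randomized subject (Protocol 9.4.1): "Subjects in the ITT population will be analyzed as randomized". Under SAP 8.3.2, "safety and efficacy data collected at early termination visits will be windowed into a scheduled study visit" when the ET falls inside that visit's window (Day 28 ±2; Day 84 -5/+2); otherwise the data are left out of summaries. Under Protocol 9.1.3 and SAP 8.3.1, the primary analysis uses available data when overall discontinuation is below 5% and multiple imputation when it is 5% or more.

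**The concern.** An all-randomized comparison needs outcomes from subjects who stopped treatment as well as from those who stayed on it. The visible collection rules do not secure these, even for subjects who still consent and could attend a visit that is already scheduled. The Schirmer is the weaker of the two primaries here, because an ET that counts as Day 28 cannot supply it.

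Stopping may be related to tolerability or lack of benefit. If so, leaving these subjects out, or imputing them from subjects who stayed on drops, can make the active arms look better than an all-randomized comparison would. An analysis plan can choose how to handle values that were collected; it cannot recover values that were not. Day 84 is affected in the same way, and both measures are secondary endpoints there.

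**Working it through.** **1. The plan's own figures.** Protocol 9.1.1: "All primary and secondary analyses will be two-sided at a significance level of 0.05". Protocol 9.3 gives ODS-VAS inputs "assuming a true difference (AR-15512 minus vehicle) of -8.5, a common standard deviation of 19.0, and a two-sided alpha = 0.05", and for the Schirmer a difference of 1.4 mm with SD 3.15 mm. Each is said to have 90% power with 108 per arm.

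n per arm = 2 × (1.960 + 1.282)² × (SD/difference)²

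- ODS-VAS: 106 per arm (t-test 106); power at 108 is 90.8% (t-test 90.5%).
- Schirmer: 107 per arm (t-test 108); power at 108 is 90.4% (t-test 90.2%).
- Dropout: 108/0.90 = 120 per arm, 360 in total.

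The sizing reproduces. It removes the 10% and applies the full effect to the rest, with no allowance for outcomes after stopping.

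**2. What is collected, by timing of exit.**

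| Exit through ET | Day 28 ODS-VAS | Day 28 Schirmer |
|---|---|---|
| Before Day 26 | Taken at ET, but cannot count as Day 28 | Not taken |
| Days 26-30, Visit 4 not done | Counts as Day 28 | Not taken |
| After Visit 4 | Already observed | Already observed |

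The pattern repeats at Day 84: an ET on Days 79 to 86 in place of Visit 5 gives the VAS but no Schirmer.

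**3. Which missing-data rule applies.** 10% of 360 is 36 subjects; the 5% trigger is 18. On the plan's own dropout assumption, multiple imputation is the primary analysis.

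**4. Illustrative overstatement.** Assumptions: a share p of active-arm subjects stops by Day 28; they truly have the vehicle-level outcome; they are imputed with the full planned effect. The documents do not give p, so 3-10% is a range chosen for illustration. The upper end places all of the planned 10%, which runs to Day 84, before Day 28.

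Overstatement = p × difference; SE = SD × √(2/108)

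- ODS-VAS: 0.03 × 8.5 = 0.26; 0.10 × 8.5 = 0.85. SE = 19 × √(2/108) = 2.59. Ratio 0.10 to 0.33.
- Schirmer: 0.03 × 1.4 = 0.04 mm; 0.10 × 1.4 = 0.14 mm. SE = 3.15 × √(2/108) = 0.43 mm. Ratio 0.10 to 0.33.

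**5. Power if everyone is measured.** With all 120 per arm measured and a share q of the active arm losing the whole effect, the difference becomes (1 - q) × the planned difference.

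| q | ODS-VAS difference, power | Schirmer difference, power |
|---|---|---|
| 5% | 8.075, 90.9% | 1.33 mm, 90.5% |
| 10% | 7.65, 87.7% | 1.26 mm, 87.3% |

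If half the effect is kept at q = 10%, power is 90.9% and 90.5%.

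**The case against.** **The documents do distinguish the two events.** Protocol 6.10 covers removal from the study or from the product, the adverse-event form in 6.9.3 has separate entries for product discontinued and interrupted, and SAP 5.1 tabulates test-agent discontinuation apart from subject discontinuation. No sentence says that stopping drops ends participation; that is inferred from where the sentence in 6.10.2 sits and from the last item of the ET list. This stands as a limit on the wording. It does not supply what is missing: the event is recorded but leads to no efficacy visit.

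**A reader might infer that outcomes after stopping are never observed and must always be imputed.** The documents do not support this. ODS-VAS is taken at ET and counts if in window, subjects who stop after Visit 4 already have both Day 28 primaries, and imputation is primary only at 5% or more.

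**A reader might also infer that the primary imputation assumes data missing at random.** The primary model, and any strategy for treatment stops, are not in the visible parts of SAP 8.3.1 and 8.4.1. For the Schirmer responder endpoints, SAP 8.4.2 names several methods, including imputation under missingness not at random.

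**The earlier study's 9.2% is tempting as an estimate.** It is 10 subjects pooled across arms: 2 on active BID, 2 on vehicle BID, 2 on vehicle TID and 4 on active TID (Protocol, Introduction). Under BID, the regimen used here, the split was 2 against 2, and the formulation has since changed. It shows that stopping occurs. It does not estimate the rate here or show imbalance.

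**Using off-treatment values is partly an estimand choice in a Phase 2b trial.** That is fair, but collecting them keeps every choice open.

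**Conclusion.** The point holds as a gap in data collection. Nothing visible asks consenting subjects who stop drops for the Day 28 or Day 84 efficacy measurements, and the ET visit omits one of the two primary endpoints even where SAP 8.3.2 would count that visit as Day 28. The affected subjects are those who exit before the Day 28 window (both primaries) and those who exit within it without Visit 4 (Schirmer only), with the same pattern at Day 84.

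The size is modest: at most about a third of a standard error under assumptions that each push it upward, and about a tenth at 3% stopping. These figures are neither forecasts nor evidence that the planned imputation is biased. The point is worth acting on because the remedy is cheap and uncollected values cannot be recovered at analysis.

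**What to change.** - In Protocol 6.10.2 and 6.10.3, define discontinuation of treatment separately from withdrawal from the study.
- Ask subjects who stop drops but keep consent for the pre-CAE ODS-VAS and the anesthetized Schirmer at the scheduled Day 28 and Day 84 visits, and use those values in the ITT analysis.
- Add the anesthetized Schirmer to the ET list and both schedules. This helps only when the ET falls inside a visit window.

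The request covers only these pre-CAE assessments and leaves the decision to stop treatment untouched. The visit lists also contain CAE exposure (Day 28 at selected sites, and Day 84) and, at Day 28, in-office administration of study treatment; the sponsor must state how those items apply to these subjects.

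The cost is a protocol amendment and already scheduled assessments for at most about 36 subjects on the plan's 10% dropout. Some will decline. Including off-treatment values may lower power, to about 87-88% at 10% stopping with full loss of effect; at 5% it is about 90.5-91%.
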